3.1. Analysis Sets

Analysis sets define the subjects to be included in an analysis. Analysis sets and their definitions are provided in this section. The analysis set will be identified and included as a subtitle of each table, figure, and listing.

For each analysis set, the number and percentage of subjects eligible for inclusion, as well as the number and percentage of subjects who were excluded and the reasons for their exclusion (if available), will be summarized by treatment group.

A listing of reasons for exclusion from analysis sets (if applicable) will be provided by subject.

3.1.1. All Enrolled Analysis Set

All Enrolled Analysis Set includes all subjects who enrolled into this study as recorded in the Enrollment eCRF.

3.1.2. Safety Analysis Set

The Safety Analysis Set includes all subjects who took at least 1 dose of study drug in Study GS-US-419-3896. This is the primary analysis set for safety and efficacy analyses.

3.1.3.

[REDACTED]

3.2. Subject Grouping

For analyses based on the Safety Analysis Set and [REDACTED], subjects will be grouped according to the actual treatment received. The actual treatment received will differ from the assigned treatment only when their actual treatment differs from assigned treatment for the entire treatment duration.

For analyses of baseline characteristics and efficacy endpoints in the subset of subjects who rolled over into the LTE due to failure to meet response/remission criteria at W10 (see Section 3.4 and Section 6.3), subjects will be grouped according to the actual treatment received in both the parent study and the LTE study.

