## **2. OBJECTIVES**

The primary objective of this study is:

- To observe the long-term safety of filgotinib in subjects who have completed or met protocol specified efficacy discontinuation criteria in a prior filgotinib treatment study for CD

The secondary objective of this study is:

- To evaluate the effect of filgotinib on PRO2 and CDAI scores

[REDACTED]

[REDACTED]

[REDACTED]

[REDACTED]

[REDACTED])

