### 3.3. Study Treatments

This is a long-term extension study. Some subjects will receive open-label drug and some will receive blinded dosing until subject's treatment in the corresponding parent study is unblinded. In general, subjects who fully complete a parent study blinded will continue blinded dosing at the same regimen in the present study on 200 mg filgotinib, 100 mg filgotinib, or placebo. After the corresponding parent study (GS-US-419-4015, GS-US-419-4016, or GS-US-419-3895, or other Gilead/ Galapagos-sponsored filgotinib treatment study) is unblinded, subjects enrolled in the present study may be unblinded. Subjects who enroll from a parent study and receive blinded treatment in the DIVERSITY LTE study will have their DIVERSITY LTE treatment assignment unblinded when the parent study is unblinded. Subjects will continue on the same dose of open-label filgotinib as they had been receiving in blinded treatment. Subjects on placebo treatment will discontinue study drug and study participation. Subjects who exit a parent study due to disease worsening or failure to meet response or remission criteria will receive open-label 200 mg filgotinib, with the exception of US and Korea males in this category who were not considered biologic refractory who will receive open-label 100 mg filgotinib. Subjects enrolled from other filgotinib treatment studies for CD will receive open-label 200 mg filgotinib daily.

For the purposes of this study, the definition of dual (or biologic) refractory includes subjects who:

- 1) Failed any TNF $\alpha$  antagonist and vedolizumab at the time of randomization in studies GS-US-419-3895, GS-US-419-4015, and GS-US-419-4016, or
- 2) Failed any TNF $\alpha$  antagonist and are taking vedolizumab at the time of randomization into the GS-US-419-4016 study.

Details on dosing regimen for LTE are noted below in [Table 3-1](#).

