**Table 3-1. Dosing Regimens in LTE**

Dose in parent study	Reason for exiting parent study	Dose in LTE	Dose in LTE after LTE Unblinding
All Females, Non-US males and US & Korea dual refractory males			
200 mg filgotinib, blinded	Study completed to end	200 mg filgotinib + PTM 100 mg (blinded dosing)	200 mg filgotinib, open-label
100 mg filgotinib, blinded	Study completed to end	100 mg filgotinib + PTM 200 mg (blinded dosing)	100 mg filgotinib, open-label
Placebo, blinded	Study completed to end	PTM 100 mg + PTM 200 mg (blinded dosing)	Discontinue study drug
200 mg filgotinib, open-label/ blinded	Completed treatment up to primary endpoint	200 mg filgotinib, open-label	200 mg filgotinib, open-label
Placebo, open-label/ blinded	Completed treatment up to primary endpoint	200 mg filgotinib, open-label	200 mg filgotinib, open-label
200 mg filgotinib, blinded	Disease worsening and/or failure to meet response/remission criteria	200 mg filgotinib, open-label	200 mg filgotinib, open-label
100 mg filgotinib, blinded	Disease worsening and/or failure to meet response/remission criteria	200 mg filgotinib, open-label	200 mg filgotinib, open-label
Placebo, blinded	Disease worsening and/or failure to meet response/remission criteria	200 mg filgotinib, open-label	200 mg filgotinib, open-label
200 mg filgotinib, open-label	Study completed to end	200 mg filgotinib, open-label	200 mg filgotinib, open-label
100 mg filgotinib, open-label	Study completed to end	100 mg filgotinib, open-label	100 mg filgotinib, open-label
200 mg filgotinib, open-label	Disease worsening and/or failure to meet response/remission criteria	200 mg filgotinib, open-label	200 mg filgotinib, open-label
100 mg filgotinib, open-label	Disease worsening and/or failure to meet response/remission criteria	200 mg filgotinib, open-label	200 mg filgotinib, open-label

Dose in parent study	Reason for exiting parent study	Dose in LTE	Dose in LTE after LTE Unblinding
US & Korea Males who have not failed at least two biologic therapies (any TNF<math>\alpha</math> and vedolizumab)			
100 mg filgotinib, blinded	Study completed to end	100 mg filgotinib (blinded dosing)	100 mg filgotinib, open-label
Placebo, blinded	Study completed to end	PTM 100 mg (blinded dosing)	Discontinue study drug
100 mg filgotinib, blinded	Disease worsening and/or failure to meet response/remission criteria	100 mg filgotinib, open-label	100 mg filgotinib, open-label

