4.2.1. Duration of Exposure to Study Drug

Total duration of exposure to study drug will be defined as last dosing date minus first dosing date plus 1, regardless of any temporary interruptions in study drug administration, and will be expressed in weeks using up to 1 decimal place (eg, 4.5 weeks). If the last study drug dosing date is missing (for subjects that have stopped treatment or the study as indicated by a study disposition record), the latest date among the treatment (study) disposition date, clinical visit date, laboratory sample collection date, and vital signs assessment date that occurred during the on-treatment period (i.e., after exposure start date) will be used for subjects included in the final analyses or the last available date in the database snapshot at the time of an interim analysis.

If month and year of the last dose are known, and the last study drug dosing date imputed above is different from the month collected, the last date of that month will be used. If only year of the last dose is known, and the last study drug dosing date imputed above is after the year collected, the last date of that year will be used; if the last study drug dosing date imputed above is before the year collected, the first date of that year will be used.

The total duration of exposure to study drug will be summarized using descriptive statistics and using the number (ie, cumulative counts) and percentage of subjects exposed through the following time periods: 1 day, 2 weeks, 4 weeks, 12 weeks, 24 weeks, 36 weeks, 48 weeks, 52 weeks, 60 weeks, and then every 12 weeks from Week 60. Summaries will be provided by treatment group for the Safety Analysis Set.

No formal statistical testing is planned.

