7.1.7.1. Summaries of AE incidence in Combined Severity Grade Subsets

A brief, high-level summary of the number and percentage of subjects who experienced at least 1 TEAE in the categories described below will be provided by treatment group. All deaths observed in the study will also be included in this summary.

The number and percentage of subjects who experienced at least 1 TEAE will be provided and summarized by SOC, PT, and treatment group. The same summary is provided for the other AE categories described below.

- TEAEs with Grade 3 or higher
- TEAEs with Grade 2 or higher
- Treatment-emergent (TE) treatment-related AEs
- TE treatment-related AEs with Grade 3 or higher
- TE treatment-related AEs with Grade 2 or higher
- TE SAEs
- TE treatment-related SAEs
- TEAEs leading to premature discontinuation of study drug
- TEAEs leading to premature discontinuation of study
- TE AEs leading to death (ie, outcome of death)
- TEAEs leading to temporary interruption of study drug

Multiple events will be counted only once per subject in each summary. Adverse events will be summarized and listed in descending order of frequency, first by SOC, then by PT and then alphabetically. For summaries by severity grade, the most severe grade will be used for those AEs that occurred more than once in an individual subject during the study.

In addition to the above summary tables, the following TEAEs will be summarized by PT only, in descending order of total frequency:

- TEAEs
- TEAEs with Grade 3 or higher
- TE SAEs
- TEAEs leading to premature discontinuation of study drug.

In addition, data listings will be provided for the following:

- All AEs, indicating whether the event is treatment emergent
- All SAEs
- All Deaths
- All SAEs leading to death (ie, outcome of death)

- All AEs with severity of Grade 3 or higher
- All AEs leading to premature discontinuation of study drug
- All AEs leading to premature discontinuation of study
- All AEs leading to temporary interruption of study drug

In addition, an XML file will be created to support EUDRACT reporting for the final analysis containing serious AEs, non-serious AEs and non-serious AEs occurring in at least 5% of subjects in at least one treatment arm, either at system organ class level or at PT level. (This XML file will be created in-house).

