7.1.8. Adverse Events of Interest

Adverse events of interest (AEI) include infections, gastrointestinal perforations, herpes zoster, malignancies (excluding non-melanoma skin cancers), non-melanoma skin cancers, major adverse cardiovascular events (MACE), and thromboembolic events. Summaries of the following treatment-emergent AEI will be produced to enhance the analysis of safety data.

- Events of infections presented in the following subcategories:
 - AEs of infections, utilizing all AEs in the MedDRA Infections and Infestations SOC
 - AEs of serious infections, using all AEs in the MedDRA Infections and Infestations SOC that are classified as SAEs
 - AEs of herpes zoster, utilizing an MST list developed by the Sponsor
 - AEs of opportunistic infections, utilizing a narrow scope SMQ
- AEs of malignancies, excluding non-melanoma skin cancers, utilizing an MST list developed by the Sponsor
- AEs of non-melanoma skin cancers, utilizing an MST list developed by the Sponsor
- AEs of gastrointestinal perforation, utilizing an MST list developed by the Sponsor
- AEs of MACE, utilizing a positively adjudicated event list, presented in the following subcategories (Section 7.1.8.1):
 - Cardiovascular (CV) death
 - Non-fatal myocardial infarction (MI)
 - Non-fatal stroke
- AEs of arterial systemic thromboembolism (ASTE), utilizing a positively adjudicated event list (Section 7.1.8.1)

- AEs of venous thromboembolism (VTE), utilizing a positively adjudicated event list, presented in the following subcategories (Section 7.1.8.1):
 - Venous Thrombotic and Embolic Events
 - Other

The number and percentage of subjects with a reported event will be summarized for each treatment group by PT for each AEI category. Data listings for AEI will also be provided.

A by-subject listing for subjects with potential events for adjudication (MACE, ASTE, and VTE) and their respective adjudication results will be provided.

A by-subject listing of thromboembolic history and risk factors will be provided for subjects with potential events for adjudication (MACE, ASTE, and VTE).

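### Adverse events are tabulated only as crude percentages by extension-study treatment, which mixes treatment with length of observation and route of entry

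*SAP*

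**What the plan says.** The primary objective (Protocol 2) reads "To observe the long-term safety of filgotinib in subjects who have completed or met protocol specified efficacy discontinuation criteria", where both conditions refer to an earlier filgotinib study. Safety is the primary endpoint.

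The safety tables are built as follows:

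- **Columns.** SAP 3.2: "subjects will be grouped according to the actual treatment received". Parent-study treatment enters the grouping only for baseline characteristics and efficacy in Week 10 non-responders. SAP 3.3 excludes covariates.
- **Adverse events.** SAP 7.1.7.1: "The number and percentage of subjects who experienced at least 1 TEAE will be provided and summarized by SOC, PT, and treatment group". The same format serves SAEs, graded, related and discontinuation events.
- **Events of interest.** SAP 7.1.8: "The number and percentage of subjects with a reported event will be summarized for each treatment group by PT for each AEI category".
- **Exposure.** SAP 4.2.1: "Summaries will be provided by treatment group for the Safety Analysis Set".

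Assignment follows Protocol 3.3 and Table 3-1. On efficacy failures: "Subjects who exit a parent study due to disease worsening or failure to meet response or remission criteria will receive open-label 200 mg filgotinib". Males from the US or Korea whose disease was not biologic refractory are treated differently: they go to 100 mg, also open-label. Placebo appears in Table 3-1 only after completion of the parent study, for example as "PTM 100 mg + PTM 200 mg (blinded dosing"). Under Protocol 6.7, placebo subjects stop drug and participation after unblinding, and filgotinib subjects stay on. Protocol 3.4 puts the longest treatment at about 7.5 years.

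**The concern.** A crude percentage rises with time under observation. Groups followed for different lengths of time will show different percentages even when their event rates are equal. Here the difference in follow-up is built into the design.

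Extension treatment is also tied to why the subject left the parent study. The placebo group is all completers, and the filgotinib groups add subjects whose disease worsened or did not respond. Failures on 100 mg are a narrower group still: US and Korean males who had not failed two biologics.

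The report will set 200 mg, 100 mg and placebo percentages next to each other for the primary endpoint. From the adverse event tables alone, a reader could not say how much of a difference reflects treatment, longer observation or a different kind of entrant. Nor could a reader find the event frequency in filgotinib-treated completers or in filgotinib-treated efficacy failures, the two kinds of entrant that the objective mentions.

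**Working it through.** The plan states no event rate, power or precision target for safety, so there is no figure to reproduce. The check is a reading of who is in each column, followed by two illustrations.

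**1. Column content (Protocol Table 3-1)**

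| Extension treatment | Completers | Efficacy failures |
|---|---|---|
| Placebo | yes | none |
| 100 mg | yes | only US/Korea males without two failed biologics |
| 200 mg | yes | from the 200 mg, 100 mg and placebo parent arms |

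All blinded rows are completers. The open-label 200 mg and 100 mg rows contain both routes.

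**2. What Section 7.1 of the SAP provides.** Sections 7.1.6 to 7.1.8 show no redaction. They contain no person-time denominator, no time-to-event summary and no split by exit route. SAP 4.1 counts subjects by exit reason, without events.

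**3. Follow-up illustration.** Assume a constant rate r and observation time T, both assumed. Crude percentage = 1 − exp(−rT).

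| r per 100 person-years | 1 year | 2 years | 4 years | 4 years ÷ 1 year |
|---|---|---|---|---|
| 1 | 1.00% | 1.98% | 3.92% | 3.9 |
| 2 | 1.98% | 3.92% | 7.69% | 3.9 |
| 5 | 4.88% | 9.52% | 18.13% | 3.7 |

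Within each row the rate per 100 person-years is the same at every T, so an exposure-adjusted rate would give a ratio of 1.0.

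**4. Case-mix illustration.** Let c be the completer rate, R the failure-to-completer rate ratio, and f the share of **person-time** in the 200 mg column contributed by failures. With no drug effect, the 200 mg rate is c(1 − f) + cRf and the placebo rate is c, so their ratio is 1 + f(R − 1). All inputs are assumed.

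| R | f = 0.25 | f = 0.50 | f = 0.75 |
|---|---|---|---|
| 0.75 | 0.94 | 0.88 | 0.81 |
| 1.5 | 1.13 | 1.25 | 1.38 |
| 2.0 | 1.25 | 1.50 | 1.75 |

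The ratio can fall on either side of 1. These are already person-time rates, so exposure adjustment alone does not remove the case-mix part. That needs the split by exit route.

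**The case against.** The strongest reply is that the SAP does what the protocol asks. Protocol 8.6.2 requires only numbers and percentages of subjects with TEAEs, and no test or comparison is planned. The objective joins the two kinds of entrant with an *or* that mirrors inclusion criterion 6, so it describes who may enrol. This stands. A reader might infer a breach of the protocol or an invalid inference, and the documents support neither.

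A reader might also infer that the two populations are never shown apart. That goes too far. The placebo group is completers only. The visible, partly redacted text of SAP 3.2 does not say whether blinded and open-label periods at one dose share a column, and if they do not, the blinded columns are completers only as well. What remains is that open-label filgotinib mixes routes under either reading.

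Part of the imbalance will be visible. SAP 4.1 gives exit reason by treatment, SAP 4.2.1 gives exposure with cumulative counts, and by-subject listings are planned. Number of subjects times mean exposure approximates person-time. It does not give time to first event, and it does not give rates by route.

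Timing matters too. The first interim coincides with the unblinding of this study (SAP 2.1), so the effect of placebo stopping falls mainly on later cuts, including the final analysis.

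Finally, the revision history records that adverse event subgroups were removed as unnecessary. That was a documented choice and not an error. It makes the exit-route split the more debatable half of this point, but it does not bear on exposure adjustment.

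**Conclusion.** The point holds in this form. For the primary endpoint, the planned side-by-side percentages combine treatment with length of observation and case mix, and no planned adverse event table gives event frequency by exit route within filgotinib. This rests on visible text in Protocol 3.3, 3.4, 6.7 and Table 3-1 and SAP 3.2, 7.1.7.1 and 7.1.8. The exact make-up of the filgotinib columns is less certain, because the column definition is not fully visible.

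Neither size nor direction can be derived from the documents. A reader might infer that the tables will make filgotinib look worse than placebo. Longer observation would push that way, but the case-mix effect could go in either direction, and the documents give no event rate for either route. The figures above (a 3.7- to 3.9-fold difference from four years against one; ratios of 0.81 to 1.75 from case mix) follow from assumed inputs. The first set also assumes a constant rate over time.

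**What to change.** 1. **Exposure-adjusted incidence (SAP 7.1.7.1, 7.1.8).** Beside the crude percentages for the TEAE overview, SAEs, deaths and each category of events of interest, add subjects with an event per 100 person-years with a 95% CI. Count person-time to the first event or to the end of the treatment-emergent period. This is the stronger half of the request and stands alone.
2. **Exit-route split.** For the same short list and for exposure (SAP 4.2.1), split within filgotinib dose by recorded reason for leaving the parent study: completed, or efficacy failure (Week 10 non-response or disease worsening). Keep the pooled columns and include a filgotinib total.
3. **Entrants from other Crohn's disease studies.** Code them by recorded exit reason, and extend the SAP 4.1 categories, which name only three parent studies. They should not all be counted as completed by default: the protocol's definition says when such a subject counts as completed, but inclusion criterion 6 also admits efficacy failures from a prior study.
4. **Reconcile SAP Section 3.** It still refers to subgroup analyses by parent-study completion status. The only related subgroup visible is Week 10 non-responders, for baseline characteristics and CDAI/PRO2.

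The cost is SAP wording and a few tables. SAP 4.1 already classifies exit reason for the three named studies, and the revision history shows that a subgroup analysis with this rationale was once drafted, which is cited here only for feasibility. The downside is sparse cells for rare events. With no events in n subjects, the exact two-sided 95% upper limit is 1 − 0.025^(1/n): 0.37% at n = 1000, 0.74% at 500, 1.46% at 250 and 3.62% at 100 (sizes below 1000 are assumed). That is why the pooled columns and the filgotinib total should stay.

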## **5. INVESTIGATIONAL MEDICINAL PRODUCTS**

### **5.1. Randomization, Blinding and Treatment Codes**

In the event of a medical emergency where breaking the blind is required to provide medical care to the subject, the investigator may obtain treatment assignment directly from the interactive web response system (IWRS) for that subject. The Sponsor recommends but does not require that the investigator contact the medical monitor before breaking the blind. Treatment assignment should remain blinded unless that knowledge is necessary to determine subject emergency medical care. The rationale for unblinding must be clearly explained in source documentation and on the eCRF, along with the date on which the treatment assignment was obtained. The investigator is requested to contact the medical monitor promptly in case of any treatment unblinding.

Blinding of study treatment is critical to the integrity of this clinical trial; therefore, if a subject's treatment assignment is disclosed to the investigator, the subject will have study treatment discontinued (unless study-wide unblinding occurs or is specific to subjects previously enrolled in a given parent study [GS-US-419-4015, GS-US-419-4016, GS-US-419-3895, or any other Gilead/Galapagos-sponsored filgotinib treatment study for CD]). All subjects will be followed until study completion unless consent to do so is specifically withdrawn by the subject.

The Sponsor may independently unblind cases for expedited reporting of suspected unexpected serious adverse reactions (SUSARs).

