1.2. Study Design

This is a long-term extension (LTE) study to evaluate the safety of filgotinib administered to subjects with CD. Some subjects will receive open-label drug and some will continue to receive the blinded study drug assigned in the parent study until subject's treatment in the corresponding parent study (GS-US-419-4015, GS-US-419-4016, or GS-US-419-3895) is unblinded. The duration of treatment is up to 432 weeks.

In general, subjects who fully complete a parent study blinded will continue blinded treatment at the same regimen in the present study on 200 mg filgotinib, 100 mg filgotinib, or placebo. Subjects who enroll from a parent study and receive blinded treatment in the GS-US-419-3896 study will have their GS-US-419-3896 treatment assignment unblinded when the parent study is unblinded. After the study unblinding, subjects will continue on the same dose of open-label filgotinib as they had been receiving in blinded treatment; whereas subjects on placebo treatment

will discontinue study drug and study participation. Subjects who exit a parent study due to disease worsening or failure to meet response or remission criteria will receive open-label 200 mg filgotinib, with the exception of US and Korea males in this category who were not considered biologic refractory who will receive open-label 100 mg filgotinib.

This study includes:

- Day 1
- Treatment Visits: Week 2, Week 4, Week 12, and then every 12 weeks thereafter
- Post-Treatment (PTx) safety assessments (30 days after the last dose of study drug) for subjects who complete all study treatment visits or discontinue early

For additional details, please see the Schedule of Assessments in [Appendix 1](#).

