7.1.3. Relationship of Adverse Events to Study Drug

Related AEs are those for which the investigator selected “Related” on the AE CRF to the question of “Related to Study Treatment.” Events for which the investigator did not record relationship to study drug will be considered related to study drug for summary purposes. However, by-subject data listings will show the relationship as missing.

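### By-drug columns pool blinded and open-label filgotinib time next to placebo that is dosed only blind, and no blinded-period display is planned

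*SAP*

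**What the plan says.** **Who is blinded, and when.** SAP 1.2 describes a mixed study: "Some subjects will receive open-label drug and some will continue to receive the blinded study drug assigned in the parent study", until the parent study is unblinded. After that "subjects will continue on the same dose of open-label filgotinib as they had been receiving in blinded treatment", whereas placebo subjects stop drug and leave. Protocol 3.3 adds the group that is never blinded in the extension: "Subjects who exit a parent study due to disease worsening or failure to meet response or remission criteria will receive open-label 200 mg filgotinib". US and Korean males who are not biologic refractory are the exception and receive open-label 100 mg. In Protocol Table 3-1, placebo appears as an extension dose only in blinded rows.

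**How columns are formed.** SAP 3.2 states that "subjects will be grouped according to the actual treatment received". Blinding status is not part of that rule.

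**What is shown in them.** SAP 7.1.3 leaves causality to the site: "Related AEs are those for which the investigator selected" the related category. SAP 7.1.7.1 tabulates by treatment group all TEAEs, related TEAEs (including "TE treatment-related AEs with Grade 3 or higher"), SAEs, and TEAEs leading to interruption or discontinuation. SAP 6.2.2 summarises and plots CDAI and PRO2 by visit and treatment group with 95% confidence intervals. The TEAE window in SAP 7.1.6.1 runs to 30 days after drug is stopped for good, with no cut at unblinding.

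**The concern.** Some of these items can move with knowledge of treatment even if the drug does nothing. Relatedness is a clinical judgement (Protocol 7.2.1). Protocol 7.6.2 and 7.6.3 link continuing, withholding or stopping drug for Grade 3 and 4 events to that judgement, so related-AE counts and some interruption and discontinuation counts can shift together. Both PRO2 subscores and three of the eight CDAI components come from the subject's daily diary (SAP Appendix 2).

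If a filgotinib column contains a large open-label share and the placebo column almost none, a gap between the two on these items has two possible sources that the table cannot separate. Unblinding is also a calendar event, while the plots run on weeks from Day 1, so each subject crosses it at a different plotted week. The secondary objective concerns the effect of filgotinib on these scores, and SAP 2.1 foresees interim results for submission or publication, where adjacent columns will be compared.

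**Working it through.** The plan gives no sample size, power or event figure on this point, so there is nothing to reproduce. The check is a trace of the rules, followed by an illustration under stated assumptions.

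**Step 1. Contents of each column (Protocol 3.3, 6.6, 6.7 and Table 3-1; SAP 1.2, 3.2)**

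| Column (inferred) | Open label from Day 1 | Blinded, then open label at same dose | Blinded, then stopped |
|---|---|---|---|
| 200 mg | Most efficacy-exit subjects; open-label completers; entrants from other CD studies | Blinded 200 mg completers | none |
| 100 mg | US and Korean males without two failed biologics who exit for efficacy; open-label 100 mg completers | Blinded 100 mg completers | none |
| Placebo | none | none | Blinded placebo completers |

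Separate columns for open-label entrants would still leave blinded completers with both kinds of time in one column.

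**Step 2. Open-label share of a filgotinib column.** Let *f* be the share of the column's person-time from subjects open label from Day 1, and *u* the share of blinded starters' time that falls after unblinding. Then

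share *s* = *f* + (1 − *f*) × *u*.

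Both inputs are assumptions.

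| | *u* = 0 | *u* = 0.25 | *u* = 0.50 | *u* = 0.75 |
|---|---|---|---|---|
| *f* = 0 | 0% | 25% | 50% | 75% |
| *f* = 0.25 | 25% | 43.8% | 62.5% | 81.3% |
| *f* = 0.50 | 50% | 62.5% | 75% | 87.5% |
| *f* = 0.75 | 75% | 81.3% | 87.5% | 93.8% |

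With *f* of 0.25 to 0.75 for 200 mg, the share is 25% to 94%. For example, 0.75 + 0.25 × 0.75 = 0.9375. Few routes lead to open-label 100 mg, so *f* is probably lower there; with *f* of 0 to 0.25 the share is 0% to 81%. At the first interim, which is timed with the GS-US-419-3895 final analysis, *u* is near 0 for completers from that study. They are still pooled with subjects open label from Day 1.

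**Step 3. The placebo column is not entirely blind.** Dosing is blinded only, but Protocol 6.6 places an early-termination visit with AEs, CDAI and PRO2 after unblinding, and TEAEs count for 30 more days. The tail's share of observation time is 30 / (blinded days + 30):

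- 0.5 year blinded: 30 / 212.6 = 14.1%
- 1 year: 30 / 395.25 = 7.6%
- 2 years: 30 / 760.5 = 3.9%
- 7.5 years: 30 / 2769.4 = 1.1%

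**Step 4. Why patient-year rates do not cure it.** Suppose AEs are equally frequent in all columns and are called related with probability *r*B when blind and *r*O when filgotinib is known. The related share is then *r*B + *s*(*r*O − *r*B) on filgotinib and, ignoring the tail, *r*B on placebo. The spurious gap is *s*(*r*O − *r*B). Dividing by exposure leaves the ratio of the two unchanged. The documents give neither probability, so the gap cannot be put in numbers.

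**Step 5. Does another planned analysis cover this?** The visible efficacy subgroup is induction non-responders (SAP 3.4, 6.3). Under Table 3-1 they all receive open-label filgotinib, so there is no extension placebo column. No visible table or sensitivity analysis uses the unblinding date.

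**The case against.** The strongest reply is that the plan makes no filgotinib-placebo comparison. The primary objective is to observe safety, no hypothesis is tested (SAP 1.3) and results are descriptive. That stands, and it limits the harm to interpretation.

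The columns are also inferred from one phrase, and parts of SAP 3 and 6 are redacted. That stands too: the point rests on the visible text.

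Several stronger readings are tempting but not supported:

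- *The SAP breaches the protocol's own blinding standard.* Protocol 5.1 does say "Blinding of study treatment is critical to the integrity of this clinical trial", but the sentence concerns disclosure of a single subject's assignment and goes on to exempt study-wide or parent-study unblinding, which is the planned event here.
- *Every placebo record is blind.* Step 3 shows otherwise.
- *Filgotinib data are largely open label.* The range in Step 2 includes shares well under half, and the 100 mg column may be mainly blinded starters.
- *Most of CDAI is self-report.* Three of eight components are diary-based.
- *Every discontinuation is a judgement.* Protocol 3.5.2 lists many mandatory stops on defined events or repeated laboratory values alongside discretionary ones.
- *The whole safety profile is affected.* Laboratory values and MACE, ASTE and VTE, which are adjudicated blind, are much less exposed, and all-cause TEAE and SAE tables do not use the relatedness call.

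Finally, a restricted display is not a clean comparison: blinded entrants are those who completed the parent study on their arm, since efficacy failures moved to open label.

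**Conclusion.** The point holds as a matter of interpretation. Under the by-drug grouping, judged and self-reported items for filgotinib come from a mixture of blinded and open-label observation, while those for placebo come almost wholly from blinded observation, and no visible display separates the two. The affected items are relatedness, discretionary interruption or discontinuation, both PRO2 subscores and three CDAI components.

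The size is unknown. The 25% to 94% range for 200 mg follows from assumed mixes, and the expectation of a smaller share for 100 mg rests on the entry rules in Table 3-1, not on counts. Nothing in the documents shows that knowledge of treatment shifted any result, and no error rate is at stake. This is a cheap improvement to the SAP, not a defect that invalidates an analysis.

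**What to change.** In SAP 3.2, 6.2.2 and 7.1.7.1, add one descriptive display limited to subjects who entered the extension on blinded dosing, in columns 200 mg, 100 mg and placebo:

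- TEAEs, related TEAEs, SAEs, and AEs leading to interruption or discontinuation, with onset before the subject's parent study was unblinded, or before the subject's own unblinding if earlier.
- CDAI and PRO2 at visits before that same date.

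Keep the pooled tables for total experience, list the treatment columns explicitly in SAP 3.2, and refer any filgotinib-placebo reading to the restricted display.

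**Cost.** SAP wording, a small set of extra outputs, and a cut-off date. Unblinding follows the parent study, so one date per parent study serves for most subjects. Protocol 5.1 requires the date of an emergency unblinding on the eCRF. The documents do not say that a planned unblinding date is held per subject in the IWRS, so the source of the date should be named.

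**Downsides to state with the display.** It will have fewer events and shorter follow-up. Its groups are parent-study completers on each arm, so it removes the blinding difference but is not a randomised comparison.
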